5.4.9. Trametinib Dose Modification for Hypertension

Increases in blood pressure (BP) have been observed in patients receiving trametinib.

Should initiation of anti-hypertensive therapy be required, single agent therapy (commonly including the calcium channel blockers amlodipine or nifedipine) should be started and the blood pressure should be monitored at least twice weekly until BP is within the 95th percentile for age, height, and gender per Appendix IX.

If patient is already on an anti-hypertensive medication at study enrollment, then their anti-hypertensive therapy should be adjusted (by either adjusting the dose of their current anti-hypertensive medication or by adding another anti-hypertensive agent) according to the algorithm in Section 5.4.9.3.

5.4.9.1. Baseline Blood Pressure

[figure not shown]
Baseline blood pressure (BP) is defined as the blood pressure obtained at the examination used for study enrollment. This baseline BP should be obtained as follows:

- Obtain 3 serial blood pressures from the same extremity with the patient in the same position that are separated by at least 5 minutes. Avoid using the lower extremity if possible.
- The baseline BP is the mean average of the systolic and the mean average of the diastolic measurements.

5.4.9.2 Management of Hypertension

- The upper limit of normal (ULN) is defined as a BP equal to the 95th percentile for age, height, and gender. ([Appendix IX](#))
- The NCI CTCAE will be utilized to determine the grade of hypertension for reporting purposes.
- Elevated BP measurements should be repeated on the same day to confirm the elevation. Patients with an elevated BP should have BP measurements performed at least twice weekly until BP is \leq ULN.
- The algorithm below will be used to manage trametinib related hypertension.
- Hypertension should be managed with appropriate anti-hypertensive agent(s) as clinically indicated. It is strongly recommended that nephrology or cardiology be consulted in the evaluation and management of hypertension.

5.4.9.3 Algorithm For Management of Trametinib-Related Hypertension

Elevations in BP are based on systolic or diastolic pressures.

†Elevated blood pressure measurements should be repeated on the same day to confirm the elevation. Patients with elevated BP at any time should have BP measurements performed at least twice weekly until BP is within the ULN.

§ULN is a BP equal to the 95th percentile for age, height, and gender-appropriate normal values ([Appendix IX](#)).

*If BP > 25 mm Hg above ULN for age (verified) or Grade 4 hypertension at any time, hold drug. Study drug should also be held for BP \geq 25 mm Hg above the ULN for 14 days or \geq 35 mm Hg above baseline for > 14 days. Antihypertensive agents can be used to control hypertension as clinically indicated after study drug is held.

^Antihypertensive therapy should be prescribed as clinically indicated, including use of multiple anti-hypertensive agents.

#Baseline BP as defined in Section 5.4.9.1

Arm 1 of algorithm:

- If blood pressure (BP) \leq 95thile for age, height, and gender: continue trametinib at the same dose.

Arm 2 of algorithm:

- If BP \leq 10 mm Hg above the ULN: continue trametinib at the same dose and recheck the BP within 72 hours.
 - If the BP is \leq ULN on recheck, continue trametinib at the same dose.
 - If the BP remains above the ULN on recheck, then start/adjust antihypertensive therapy and follow Arm 3 of the algorithm from the point that anti-hypertensive therapy is started/adjusted.

Arm 3 of algorithm:

- If BP is 11 to 25 mm Hg above the ULN on \geq 2 of 3 measurements or $>$ 35 mmHg above baseline on \geq 2 of 3 measurements, start/adjust anti- hypertensive therapy and continue trametinib at the same dose. Monitor BP at least twice weekly.
 - If the BP returns to \leq ULN within 14 days, continue trametinib at the same dose and continue anti-hypertensive therapy.
 - If the BP remains elevated \geq 25 mmHg above the ULN or $>$ 35 mmHg above baseline for more than 14 days after the institution/adjustment of anti-hypertensive therapy, **hold trametinib**, monitor BP at least every 3 days, and follow Arm 4 of the algorithm from the point that trametinib is held. The anti-hypertensive therapy should be continued until the BP is less than the ULN.
- If the BP returns to \leq ULN within 14 days, restart trametinib at reduced dose (25% dose reduction in patients receiving oral solution or at specified dose reduction in patients receiving tablets (See [Appendix II](#)).
- If the BP remains $>$ ULN for more than 14 days, patient must be removed from protocol therapy.
 - If the BP increases to $>$ 25 mm Hg above the ULN despite anti-hypertensive therapy, hold trametinib, but continue the anti-hypertensive agent(s). Monitor the BP as clinically indicated and follow Arm 4 of the algorithm from the point that trametinib is held.

Arm 4 of algorithm:

- If BP is $>$ 25 mm Hg above the ULN **hold** trametinib, monitor BP, and administer/adjust anti-hypertensive therapy as clinically indicated.
 - If the BP returns to \leq ULN within 14 days, trametinib may be restarted at a reduced dose.
 - If the BP is $>$ ULN for $>$ 14 days, the patient must be removed from protocol therapy

Arm 5 of algorithm:

If the participant develops Grade 4 hypertension, discontinue trametinib, monitor BP and administer anti-hypertensive therapy as clinically indicated. The patient is Off Protocol Therapy.

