3.3.4 Patients who in the opinion of the investigator may not be able to comply with the safety monitoring requirements of the study are not eligible.

3.3.5 Venous-occlusive Disease: Patients with a history of hepatic sinusoid obstructive syndrome (veno-occlusive disease) within the prior 3 months are not eligible.

3.3.6 Patients with a history of or current evidence/risk of retinal vein occlusion (RVO) or central serous retinopathy (CSR) are not eligible.

3.3.6.1 Ocular Conditions: Patients with a history of RVO or CSR, or predisposing factors to RVO or CSR (e.g., uncontrolled glaucoma or ocular hypertension).

3.3.7 Systemic Diseases: Patients with uncontrolled systemic disease(s) such as hypertension or diabetes mellitus are not eligible. Blood pressure must be \leq the 95th percentile for age, height, and gender ([Appendix IX](#)) measured as described

in [Section 5.4.9.1](#).

3.3.8 Allergic Reactions: Patients with a history of allergic reaction attributed to compounds of similar chemical or biologic composition to the MEK inhibitor, trametinib are not eligible.

3.3.9 Noonan Syndrome: Patients with a clinical diagnosis of Noonan syndrome are not eligible. **Note**: patients with Casitas B-lineage lymphoma (CBL) syndrome, also known as Noonan-like syndrome, are eligible to enroll.

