APPENDIX IX: BLOOD PRESSURE LEVELS FOR CHILDREN BY AGE AND HEIGHT PERCENTILE

Blood pressure (BP) levels for BOYS:

Age (years)	BP Percentile	Systolic Blood Pressure, mm Hg							Diastolic Blood Pressure, mm Hg						
		Percentile of Height													
		5th	10th	25th	50th	75th	90th	95th	5th	10th	25th	50th	75th	90th	95th
1	95th	98	99	101	103	104	106	106	54	54	55	56	57	58	58
2	95th	101	102	104	106	108	109	110	59	59	60	61	62	63	63
3	95th	104	105	107	109	110	112	113	63	63	64	65	66	67	67
4	95th	106	107	109	111	112	114	115	66	67	68	69	70	71	71
5	95th	108	109	110	112	114	115	116	69	70	71	72	73	74	74
6	95th	109	110	112	114	115	117	117	72	72	73	74	75	76	76
7	95th	110	111	113	115	117	118	119	74	74	75	76	77	78	78
8	95th	111	112	114	116	118	119	120	75	76	77	78	79	79	80
9	95th	113	114	116	118	119	121	121	76	77	78	79	80	81	81
10	95th	115	116	117	119	121	122	123	77	78	79	80	81	81	82
11	95th	117	118	119	121	123	124	125	78	78	79	80	81	82	82
12	95th	119	120	122	123	125	127	127	78	79	80	81	82	82	83
13	95th	121	122	124	126	128	129	130	79	79	80	81	82	83	83
14	95th	124	125	127	128	130	132	132	80	80	81	82	83	84	84
15	95th	126	127	129	131	133	134	135	81	81	82	83	84	85	85
16	95th	129	130	132	134	135	137	137	82	83	83	84	85	86	87
17	95th	131	132	134	136	138	139	140	84	85	86	87	87	88	89

Instructions for using this BP Chart:

1. Measure the patient’s blood pressure using an appropriate size cuff.
2. Select appropriate chart for female or male patient.
3. Using the “age” row and “height” column determine if the BP is within the ULN.
4. See [Section 5.1.1](#) for definition of dose limiting hypertension. See [Section 5.4.9.2](#) for management and grading of hypertension.

This table was taken from “The Fourth Report on the Diagnosis, Evaluation, and Treatment of High Blood Pressure in Children and Adolescents” PEDIATRICS Vol. 114 No. 2 August 2004, pp. 555-576.

Note: For patients ≥ 18 yrs, ULN BP is 140/90 mmHg.

Blood pressure (BP) levels for GIRLS:

Age (years)	BP Percentile	Systolic Blood Pressure, mm Hg							Diastolic Blood Pressure, mm Hg						
		Percentile of Height							Percentile of Height						
		5th	10th	25th	50th	75th	90th	95 th	5th	10th	25th	50th	75th	90th	95 th
1	95th	100	101	102	104	105	106	107	56	57	57	58	59	59	60
2	95th	102	103	104	105	107	108	109	61	62	62	63	64	65	65
3	95th	104	104	105	107	108	109	110	65	66	66	67	68	68	69
4	95th	105	106	107	108	110	111	112	68	68	69	70	71	71	72
5	95th	107	107	108	110	111	112	113	70	71	71	72	73	73	74

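### The hypertension algorithm gives two dispositions for Grade 4 events, leaves some persistent Arm 3 elevations without a study-drug decision, and has no ULN values under age 1

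*Combined protocol and SAP*

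**What the plan says.** **Grade 4.** A footnote in section 5.4.9.3 pairs two triggers, a verified pressure more than 25 mm Hg above ULN and Grade 4 hypertension, with one action: "Grade 4 hypertension at any time, hold drug". Arm 5 of the same section reads "If the participant develops Grade 4 hypertension, discontinue trametinib, monitor BP and administer anti-hypertensive therapy as clinically indicated" and then "The patient is Off Protocol Therapy". Section 5.1.1 lists Grade 4 hypertension as dose-limiting. Section 5.3 handles a non-hematological dose-limiting toxicity by a hold, with restart at a reduced dose allowed if it resolves within 14 days.

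**Arm 3.** Entry is "If BP is 11 to 25 mm Hg above the ULN on" at least two of three measurements, or more than 35 mm Hg above baseline on at least two of three. Trametinib continues while antihypertensive therapy is started or adjusted. Three branches follow:

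- return to ULN or below within 14 days: continue at the same dose;
- at least 25 above ULN, or more than "35 mmHg above baseline for more than 14 days after the institution/adjustment of anti-hypertensive therapy": hold and go to Arm 4;
- a rise to more than 25 above ULN despite therapy: hold and go to Arm 4, with no waiting period.

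**Reference values.** Section 5.4.9.2 sets the ULN at the 95th percentile in Appendix IX. Section 3.3.7 requires pressure at or below "the 95th percentile for age, height, and gender", citing the same appendix. Appendix IX has rows for ages 1 to 17 in each sex and a note for 18 and over. Section 3.2.1 admits patients from 1 month of age.

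**The concern.** A site that follows the footnote and section 5.3 could restart a patient after a Grade 4 event. A site that follows Arm 5 must remove that patient. In Arm 3, a child whose pressure settles at a raised level below the hold thresholds is neither recovered nor held, and the text does not say what happens to study drug. For an infant, a site cannot look up the number that decides eligibility or most of the algorithm.

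Section 3.3 says the exclusion criteria are read literally and cannot be waived, so a criterion with no value for part of the eligible age range is a practical problem. Amendment #1 (section 2.6) lowered the age limit from 2 years to 1 month. The creatinine table in section 3.2.5.2 has rows from 1 month, so infant limits were supplied there but not for blood pressure.

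Section 5 removals end protocol therapy (section 8.1), and best response is judged over 12 cycles (section 9.3) in 20 planned patients with a cutoff of 3 responders (section 9.2). At that size, holds and removals should not depend on which sentence a site reads.

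**Working it through.** The plan states no figure to reproduce here. Parts 1 and 3 are comparisons of text; part 2 can be enumerated.

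**Part 1: Grade 4, side by side.**

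| Source | Action | Restart possible? |
|---|---|---|
| 5.4.9.3 footnote | hold | not stated |
| 5.4.9.3 Arm 5 | discontinue, off protocol therapy | no |
| 5.1.1 with 5.3 (general dose-limiting rule) | hold | yes, reduced dose, if resolved within 14 days |

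The other trigger in the same footnote sentence, more than 25 above ULN, leads through Arm 4 to a possible restart. So a hold in this section does not by itself mean permanent removal.

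**Part 2: Arm 3.** Work in whole mm Hg. Let e = current pressure − ULN and d = ULN − baseline. Section 3.3.7 caps baseline at the 95th percentile, so d ≥ 0. Pressure above baseline is then e + d.

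- Held at once: e > 25.
- Arm 3 entry: 11 ≤ e ≤ 25, or e + d > 35 with e ≤ 25.
- Arm 3 hold after more than 14 days: e ≥ 25, or e + d > 35.

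*ULN limb.* It needs e ≥ 25 while the immediate hold needs e > 25. Only e = 25 is left, which is 1 of the 15 values from 11 to 25.

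*Baseline limb.* It needs e > 35 − d. With e at most 25, this is possible only if d > 10.

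| Baseline below ULN (d) | Values of e from 11 to 25 meeting either limb | Values from 11 to 25 with no study-drug decision |
|---|---|---|
| 0 to 11 | 1 of 15 | 11 to 24 |
| 12 | 2 of 15 | 11 to 23 |
| 15 | 5 of 15 | 11 to 20 |
| 20 | 10 of 15 | 11 to 15 |
| 24 | 14 of 15 | 11 |
| 25 | 15 of 15 | none |

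The documents give no distribution of baseline pressure, so d is shown as a range. Patients sent on from Arm 2, at up to 10 above ULN, can fall in the same gap: at d = 20, e = 10 gives e + d = 30, which meets neither limb and is still above ULN.

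*Example from Appendix IX.* A boy aged 3 at the 50th height percentile has a systolic ULN of 109, so the immediate hold starts above 134. With baseline 90, the baseline limb needs more than 125 and is met at 126 to 134 (17 to 25 above ULN); 120 to 125 is uncovered. With baseline 100, it needs more than 135 and cannot be met before the immediate hold; 120 to 133 is uncovered.

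*Footnote against Arm 3.* The footnote holds drug at 25 or more above ULN for 14 days, or 35 or more above baseline for more than 14 days. Arm 3 asks for more than 14 days on both limbs and for strictly more than 35 above baseline. The boundary cases differ.

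**Part 3: ages 1 to 11 months.**

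| Rule | Needs an Appendix IX value? |
|---|---|
| Exclusion criterion 3.3.7 | yes |
| Dose-limiting hypertension, more than 25 above the 95th percentile (5.1.1) | yes |
| ULN-based parts of Arms 1 to 4 | yes |
| Arm 3 limb on more than 35 above baseline | no |
| Arm 5 and Grade 4 dose-limiting hypertension (CTCAE grade) | no |

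**The case against.** **Hold and discontinue are compatible.** Stopping drug satisfies both sentences. Arm 5 is the specific disposition, and section 5.1.1 refers toxicities of special interest to section 5.4. This is a fair reading, and many sites would adopt it. But no sentence says that Arm 5 overrides the footnote or section 5.3, and the footnote gives Grade 4 the same action as an event that allows restart. A flow diagram may accompany this section and show what the footnote attaches to; it could clarify the intent but would not change the printed instructions.

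**Arm 3 is not silent on care.** It calls for antihypertensive therapy and monitoring at least twice weekly, and section 5.4.9.2 strongly recommends specialist input. That stands: only the study-drug decision is missing. One could say the default is to continue at the same dose, as Arm 3 opens. That is plausible, but after 14 days the text states continuation only for pressure back at or below ULN.

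**The removal line covers the gap.** Removal for pressure above ULN for more than 14 days is paired with a restart instruction and follows the hold, so it reads as applying to patients already held.

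**The hold can be met.** A reader might infer from the empty ULN limb that almost no Arm 3 patient can reach the 14-day hold. The documents do not support that. The baseline limb is also an entry route, it is reachable whenever baseline is more than 10 mm Hg below ULN, and at 25 below it captures every value from 11 to 25.

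**Conclusion.** All three points hold in limited form and should be corrected. Grade 4 hypertension has two printed dispositions. In Arm 3 the ULN limb reduces to a single value, and the zone without a study-drug decision runs from 14 of the 15 entry values (baseline within 11 of ULN) to none of them (baseline 25 below). The share of patients affected is unknown because baseline pressures are not given. The ULN-based rules have no tabulated value for ages 1 to 11 months.

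Three further inferences are not supported:

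- that one reading can lead to hold, removal or no action. Hold versus removal concerns Grade 4 events, and the missing decision concerns pressures that meet neither Arm 3 limb;
- that every arm fails for infants. Arm 5 and the baseline limb do not use the table;
- that the Bayesian toxicity monitoring is distorted. Section 9.3 lists hypertension as a monitored toxicity, but nothing there ties the count to the arms of this algorithm.

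**What to change.** Reconcile the section 5.4.9.3 footnote with Arm 5 and with section 5.3, so that Grade 4 hypertension has one stated disposition. Reconcile the Arm 3 persistence criterion with the Arm 3 entry range, so that pressure still above ULN after 14 days always has a stated study-drug decision. Align the thresholds and durations in the footnote with those in Arm 3. Name in Appendix IX a source of 95th-percentile values for ages 1 to 11 months. Which dispositions and thresholds to use is for the study team.

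The cost is an amendment to protocol wording and one reference table or citation. Sample size, endpoints and analysis are unchanged.

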6.0 DRUG INFORMATION

6.1 Trametinib

(06/09/22)

(Mekinist®, GSK1120212, TMT212-NXA, JTP-74057, JTP-78296, JTP-75303, NSC 763093)

Source and Pharmacology:

Trametinib dimethyl sulfoxide is a kinase inhibitor. The chemical name is acetamide, N-[3-[3-cyclopropyl-5-[(2-fluoro-4-iodophenyl)amino]-3,4,6,7-tetrahydro-6,8-dimethyl-2,4,7-trioxopyrido[4,3-d]pyrimidin-1(2H)-yl]phenyl]-, compound with 1,1'-sulfanylbis[methane] (1:1). It has a molecular mass of 693.53. Trametinib dimethyl sulfoxide is a white to almost white powder. It is practically insoluble in the pH range of 2 to 8 in aqueous media.

Trametinib is an orally bioavailable, reversible, highly selective allosteric inhibitor of MEK1/2 that is active in inhibition of pERK and growth of BRAF and Ras mutant cancer cell lines and hematopoietic cancer cells from acute myeloid leukemia (AML) and chronic myeloid leukemia (CML) origins. Tumor cells commonly have hyperactivated extracellular signal-related kinase (ERK) pathways in which MEK is a critical component. Trametinib dimethyl sulfoxide inhibits activation of MEK by RAF kinases and MEK kinases. Through inhibition of MEK 1 and 2 kinase activity, trametinib causes decreased cellular proliferation, Gap-1 (G1) cell cycle arrest, and increased apoptosis in vivo following oral dosing. Trametinib is FDA-approved for the treatment of adults with advanced melanoma with a BRAF V600E or V600K mutation.

Pharmacokinetics (PK):

In patients with solid tumors trametinib is absorbed rapidly with median time to maximum plasma concentration (T_{max}) occurring 1.5 hours after single oral administration of trametinib under fasting conditions. It has a moderate to high absolute oral bioavailability (72%) relative to a co-administered intravenous (IV) microdose. Single-dose administration of trametinib with a high-fat, high-calorie meal resulted in a 70% decrease in C_{max}, a 24% decrease in area under the concentration-time curve from time zero (pre-dose) to last time point (AUC_[0-t]) and a 10% decrease in AUC extrapolated to infinity (AUC_[0-∞]) compared to fasted conditions.

Following repeat-dosing the mean AUC [0-t_r] and C_{max} increased in an approximately dose proportional manner. Trametinib accumulates with repeat dosing and has a terminal half-life (T_{1/2}) of 5.3 days determined after single dose administration. Steady state appears to be achieved by Day 15, with little difference in pre-dose (trough) concentration at the end of the dosing interval (C-t_r), C_{max} and AUC [0-24]) between Days 15 and 21.

Trametinib is a low extraction ratio drug based on plasma IV clearance of 3.21 L/hr and has a high volume of distribution (V_d) of 1060 L. Following a single dose of [¹⁴C]-trametinib, approximately 50% of circulating radioactivity is represented as the parent compound. The fecal route was the major excretion pathway of radioactivity after a single [¹⁴C] trametinib oral dose, while urinary excretion accounted for up to 19% of excreted radioactivity recovered.

Potential Drug Interactions:

In vitro and in vivo data suggest that trametinib is unlikely to affect the PK of other drugs and that the PK of trametinib is unlikely to be affected by other drugs. . *In vitro* studies suggest that trametinib is not a substrate of CYP enzymes or of human BCRP, MRP2, OATP1B1, OATP1B3, OATP2B1, OCT1 or MATE1 transporters. It is eliminated predominantly via deacetylation to metabolite M5, which is mediated by carboxylesterases (CES1b, CES1c, CES2). There is little evidence from clinical studies for drug interactions mediated by carboxylesterases. Trametinib is a substrate for P-gp and BSEP, but this is not expected to be clinically relevant.

Trametinib dimethyl sulfoxide is an *in vitro* inhibitor of CYP 2C8 and is anticipated to have overall low potential for drug interactions as a perpetrator. It is also a weak CYP 2B6 and 3A4 inducer and expected to have little clinical effect on sensitive substrates. Trametinib is not an inhibitor of CYP 1A2, 2A6, 2B6, 2C9, 2C19, 2D6 and 3A4 and not an inhibitor of MRP2 or BSEP, but an *in vitro* inhibitor of P-gp, BCRP, OATP1B1, OATP1B3, OAT1, OAT3, OCT2 and MATE1 at systemic concentrations that are not clinically relevant. No clinically relevant inhibition by trametinib is predicted in the liver or kidney and a low risk of intestinal drug-drug interaction is possible with BCRP.

Trametinib is highly bound to plasma proteins (97.3%) and has the potential to interfere with other highly protein-bound drugs. Use caution in patients taking concomitant drugs that are highly protein-bound and have narrow therapeutic ranges.

Pregnancy and lactation:

Trametinib may impair female fertility in humans based on the reduction of corpora lutea in rats. Trametinib is unlikely to affect male fertility. Based on findings from animal studies and its mechanism of action, trametinib can cause fetal harm when administered to a pregnant woman. There are no adequate and well-controlled studies of trametinib in pregnant women. Women of childbearing potential should be advised to use effective contraception during treatment with trametinib and for 4 months after the last dose. Male patients must use a condom during intercourse and not to father a child during therapy and for 4 months following discontinuation of trametinib to avoid unnecessary exposure of trametinib to the fetus. It is not known if trametinib is excreted in milk. Women should not breastfeed during treatment with trametinib and for 4 months following the last dose.

Toxicity:

Comprehensive Adverse Events and Potential Risks list (CAEPR) for Trametinib dimethyl sulfoxide (GSK1120212B, NSC 763093)

The Comprehensive Adverse Events and Potential Risks list (CAEPR) provides a single list of reported and/or potential adverse events (AE) associated with an agent using a uniform presentation of events by body system. In addition to the comprehensive list, a subset, the Specific Protocol Exceptions to Expedited Reporting (SPEER), appears in a separate column and is identified with bold and italicized text. This subset of AEs (SPEER) is a list of events that are protocol specific exceptions to expedited reporting to NCI (except as noted below). Refer to the 'CTEP, NCI Guidelines: Adverse Event Reporting Requirements' http://ctep.cancer.gov/protocolDevelopment/electronic_applications/docs/aeguidelines.pdf for further clarification. *Frequency is provided based on 1111 patients.* Below is the CAEPR for Trametinib (GSK1120212B).

NOTE: Report AEs on the SPEER **ONLY IF** they exceed the grade noted in parentheses next to the AE in the SPEER. If this CAEPR is part of a combination protocol using multiple investigational agents and has an AE listed on different SPEERs, use the lower of the grades to determine if expedited reporting is required.

Version 2.6, October 10, 2019¹

Adverse Events with Possible Relationship to Trametinib (GSK1120212B) (CTCAE 5.0 Term) [n= 1111]			Specific Protocol Exceptions to Expedited Reporting (SPEER)
Likely (>20%)	Less Likely (<=20%)	Rare but Serious (<3%)	
BLOOD AND LYMPHATIC SYSTEM DISORDERS			
	Anemia		Anemia (Gr 3)
CARDIAC DISORDERS			
		Heart failure	
		Left ventricular systolic dysfunction	
	Sinus bradycardia		
EYE DISORDERS			
	Blurred vision		
	Dry eye		
		Eye disorders - Other (chorioretinopathy also known as retinal pigment epithelial detachment)	
		Eye disorders - Other (retinal vein occlusion)	
	Eye disorders - Other (visual disorders) ²		
		Papilledema	
	Periorbital edema		
GASTROINTESTINAL DISORDERS			
	Abdominal pain		Abdominal pain (Gr 2)
		Colitis	
		Colonic perforation	
	Constipation		Constipation (Gr 2)
Diarrhea			Diarrhea (Gr 3)
	Dry mouth		Dry mouth (Gr 2)
	Dyspepsia		Dyspepsia (Gr 2)
	Mucositis oral		Mucositis oral (Gr 3)
Nausea			Nausea (Gr 3)
	Vomiting		Vomiting (Gr 3)
GENERAL DISORDERS AND ADMINISTRATION SITE CONDITIONS			
	Chills		Chills (Gr 2)
	Edema face		
Fatigue			Fatigue (Gr 3)
	Fever		Fever (Gr 2)
Generalized edema ³			Generalized edema³ (Gr 2)
IMMUNE SYSTEM DISORDERS			
	Allergic reaction ⁴		
INFECTIONS AND INFESTATIONS			
	Folliculitis		Folliculitis (Gr 2)
	Lung infection		

Adverse Events with Possible Relationship to Trametinib (GSK1120212B) (CTCAE 5.0 Term) [n= 1111]			Specific Protocol Exceptions to Expedited Reporting (SPEER)
Likely (>20%)	Less Likely (<=20%)	Rare but Serious (<3%)	
	Paronychia		Paronychia (Gr 2)
	Skin infection		Skin infection (Gr 2)
INVESTIGATIONS			
	Alanine aminotransferase increased		Alanine aminotransferase increased (Gr 3)
	Alkaline phosphatase increased		Alkaline phosphatase increased (Gr 2)
	Aspartate aminotransferase increased		Aspartate aminotransferase increased (Gr 3)
	CPK increased		
	Ejection fraction decreased		
METABOLISM AND NUTRITION DISORDERS			
	Anorexia		Anorexia (Gr 3)
	Dehydration		Dehydration (Gr 3)
	Hypoalbuminemia		
	Hypomagnesemia		Hypomagnesemia (Gr 2)
	Hyponatremia		Hyponatremia (Gr 3)
MUSCULOSKELETAL AND CONNECTIVE TISSUE DISORDERS			
	Arthralgia		
	Back pain		Back pain (Gr 2)
	Pain in extremity		Pain in extremity (Gr 2)
		Rhabdomyolysis	
NERVOUS SYSTEM DISORDERS			
	Dizziness		Dizziness (Gr 2)
	Headache		Headache (Gr 2)
RESPIRATORY, THORACIC AND MEDIASTINAL DISORDERS			
	Cough		Cough (Gr 2)
	Dyspnea		Dyspnea (Gr 3)
		Pneumonitis	
SKIN AND SUBCUTANEOUS TISSUE DISORDERS			
	Alopecia		Alopecia (Gr 2)
	Dry skin		Dry skin (Gr 2)
	Nail changes		
		Palmar-plantar erythrodysesthesia syndrome	
	Pruritus		Pruritus (Gr 2)
		Skin and subcutaneous tissue disorders - Other (drug reaction with eosinophilia and systemic symptoms [DRESS])	
Skin and subcutaneous tissue disorders - Other (rash) ⁵			Skin and subcutaneous tissue disorders - Other (rash)⁵ (Gr 3)
		Stevens-Johnson syndrome ⁶	
VASCULAR DISORDERS			
	Hypertension		Hypertension (Gr 3)
		Thromboembolic event (venous)	
	Vascular disorders - Other (hemorrhage) ⁷		

¹This table will be updated as the toxicity profile of the agent is revised. Updates will be distributed to all Principal Investigators at the time of revision. The current version can be obtained by contacting [contact]. Your name, the name of the investigator, the protocol and the agent should be included in the e-mail.

²Visual disorders include visual disturbance that can be associated with conjunctival hemorrhage, corneal graft rejection, cyclitis, eye nevus, halo vision, iritis, macular edema, retinal hemorrhage, visual acuity reduced, visual impairment, and vitreous detachment.

³Generalized edema includes edema, lymphedema, and edema limbs.

⁴Hypersensitivity (allergic reactions) may present with symptoms such as fever, rash, increased liver function tests, and visual disturbances.

⁵Skin and subcutaneous tissue disorders - Other (rash) may include rash, rosacea, rash acneiform, erythematous rash, genital rash, rash macular, exfoliative rash, rash generalized, erythema, rash papular, seborrheic dermatitis, dermatitis psoriasiform, rash follicular, skin fissures, and skin chapped.

⁶Stevens-Johnson syndrome has been observed in patients treated with trametinib and dabrafenib combination.

⁷The majority of hemorrhage events were mild. Major events, defined as symptomatic bleeding in a critical area or organ (e.g., eye, GI hemorrhage, GU hemorrhage, respiratory hemorrhage), and fatal intracranial hemorrhages have been reported.

Adverse events reported on trametinib dimethyl sulfoxide (GSK1120212B) trials, but for which there is insufficient evidence to suggest that there was a reasonable possibility that trametinib dimethyl sulfoxide (GSK1120212B) caused the adverse event:

BLOOD AND LYMPHATIC SYSTEM DISORDERS - Disseminated intravascular coagulation; Febrile neutropenia; Leukocytosis

CARDIAC DISORDERS - Atrial fibrillation; Cardiac arrest; Myocardial infarction; Restrictive cardiomyopathy; Sinus tachycardia

EYE DISORDERS - Corneal ulcer; Eyelid function disorder; Flashing lights; Floaters; Glaucoma; Photophobia

GASTROINTESTINAL DISORDERS - Ascites; Duodenal ulcer; Esophageal necrosis; Esophageal ulcer; Esophagitis; Gastric hemorrhage⁷; Gastric ulcer; Gastritis; Gastrointestinal disorders - Other (intestinal obstruction); Gastrointestinal disorders - Other (pneumatosis intestinalis); Gastrointestinal fistula; Gingival pain; Hemorrhoidal hemorrhage⁷; Ileus; Obstruction gastric; Pancreatitis; Small intestinal obstruction

GENERAL DISORDERS AND ADMINISTRATION SITE CONDITIONS - Flu like symptoms; General disorders and administration site conditions - Other (axillary pain); Localized edema; Malaise; Non-cardiac chest pain; Pain

HEPATOBIILIARY DISORDERS - Cholecystitis; Hepatic failure; Hepatic pain; Hepatobiliary disorders - Other (hepatic encephalopathy)

INFECTIONS AND INFESTATIONS - Biliary tract infection; Catheter related infection; Device related infection; Endocarditis infective; Enterocolitis infectious; Hepatitis viral; Infections and infestations - Other (abscess limb); Infections and infestations - Other (necrotizing fasciitis); Infections and infestations - Other (oral infection); Pharyngitis; Sepsis; Upper respiratory infection; Urinary tract infection

INJURY, POISONING AND PROCEDURAL COMPLICATIONS - Bruising

INVESTIGATIONS - Blood bilirubin increased; Blood lactate dehydrogenase increased; Creatinine increased; Electrocardiogram QT corrected interval prolonged; GGT increased; Lipase increased;

Lymphocyte count decreased; Platelet count decreased; Serum amylase increased; White blood cell decreased

METABOLISM AND NUTRITION DISORDERS - Hyperglycemia; Hyperkalemia; Hyperphosphatemia; Hyperuricemia; Hypocalcemia; Hypoglycemia; Hypokalemia

MUSCULOSKELETAL AND CONNECTIVE TISSUE DISORDERS - Generalized muscle weakness; Muscle cramp; Musculoskeletal and connective tissue disorder - Other (compression fracture); Myalgia; Neck pain

NEOPLASMS BENIGN, MALIGNANT AND UNSPECIFIED (INCL CYSTS AND POLYPS) - Tumor hemorrhage⁷; Tumor pain

NERVOUS SYSTEM DISORDERS - Dysgeusia; Encephalopathy; Intracranial hemorrhage⁷; Lethargy; Nervous system disorders - Other (diplopia); Seizure; Somnolence; Stroke; Syncope; Transient ischemic attacks

PSYCHIATRIC DISORDERS - Anxiety; Confusion; Delirium; Depression; Hallucinations; Insomnia; Personality change

RENAL AND URINARY DISORDERS - Acute kidney injury; Cystitis noninfective; Dysuria; Hematuria; Proteinuria; Urinary incontinence

REPRODUCTIVE SYSTEM AND BREAST DISORDERS - Vaginal fistula; Vaginal hemorrhage⁷

RESPIRATORY, THORACIC AND MEDIASTINAL DISORDERS - Bronchopulmonary hemorrhage⁷; Hypoxia; Laryngeal edema; Oropharyngeal pain; Pleural effusion; Pneumothorax; Productive cough; Pulmonary hypertension; Respiratory failure; Sinus disorder

SKIN AND SUBCUTANEOUS TISSUE DISORDERS - Bullous dermatitis; Photosensitivity; Purpura; Skin and subcutaneous tissue disorders - Other (erythema nodosum); Skin ulceration; Urticaria

VASCULAR DISORDERS - Hematoma; Hot flashes; Hypotension

Note: Trametinib (GSK1120212B) in combination with other agents could cause an exacerbation of any adverse event currently known to be caused by the other agent, or the combination may result in events never previously associated with either agent.

Formulation and Stability:

Trametinib will be supplied as 0.5 mg and 2 mg (as free base) tablets and powder for oral solution. Tablets may be provided in investigationally-labeled bottles or commercially-labeled bottles.

The tablet core contains mannitol, microcrystalline cellulose, hypromellose, croscarmellose sodium, magnesium stearate (vegetable source), colloidal silicon dioxide and sodium lauryl sulfate.

The aqueous film coating consists of hypromellose, titanium dioxide, polyethylene glycol, iron oxide yellow (0.5 mg tablet), iron oxide red (2 mg tablet) and polysorbate 80 (2 mg tablet).

Each investigationally-labeled bottle contains 32 tablets with a desiccant:

- 0.5 mg tablets are yellow, modified oval, biconvex and film-coated.
- 2 mg tablets are pink, round, biconvex and film-coated.

Each commercially-labeled bottle contains 30 tablets with a desiccant:

- 0.5 mg tablets are yellow, modified oval, biconvex, film-coated tablets with 'GS' debossed on one face and 'TFC' on the opposing face.

2 mg tablets are pink, round, biconvex, film-coated tablets with 'GS' debossed on one face and 'HMJ' on the opposing face.

Trametinib tablets are immediate release for oral administration containing trametinib dimethyl sulfoxide equivalent to 0.5 mg or 2 mg of trametinib as free base.

Trametinib powder for oral solution: each bottle of powder for solution contains 5 mg supplied as a multi-dose formulation in amber glass (USP Type III) bottles with child-resistant, high-density polypropylene closures. The powder for oral solution is uniform white to slightly colored and contains 5 mg of trametinib in addition to beta-cyclodextrin sulfobutylether, sucralose, citric acid, sodium phosphate (dibasic, anhydrous), strawberry flavor, potassium sorbate and methylparaben. The oral solution is stable for 35 days after reconstitution.

Storage:

Store tablets at 2°C -8°C (36° F to 46° F) in the original bottle and dispense unopened bottles. Do not open bottles or repackage tablets or remove desiccant. Bottles should be protected from light and moisture. Refer to the package label for expiration. Stability studies are ongoing. Tablets are only stable for 32 days once bottle has been opened. If multiple bottles are dispensed to a patient in the same visit, please advise the patient to open only one bottle at a time.

Store 5 mg powder for oral solution up to 2°C - 8°C (36°F - 46°F). The oral solution (0.05 mg/mL) is stable for 35 days after reconstitution when stored up to 25°C and protected from light. Do not freeze.

If a storage temperature excursion is identified, promptly return trametinib to 2°C -8°C and quarantine the supplies. Provide a detailed report of the excursion (including documentation of temperature monitoring and duration of the excursion) to [contact] for determination of suitability.

Guidelines for Administration: See Treatment and Dose Modification sections of the protocol.

Trametinib should be taken by mouth on an empty stomach, at least 1 hour before or 2 hours after a meal. Trametinib solution can be administered via NG or G-tube, if oral administration is not feasible. Do not take a missed dose of trametinib within 12 hours of the next scheduled dose. If vomiting occurs after taking oral solution formulation, the dose of trametinib should NOT be repeated and the next dose should be administered at the regularly scheduled time. If vomiting occurs within 30 minutes of taking the tablet formulation, the dose of trametinib can be repeated once.

Reconstitution and administration of powder for oral solution:

1. Tap the sides of the Powder-in-Bottle to loosen the powder, and then remove the cap. Add 90 mL room-temperature water for irrigation, bottled still drinking water, Sterile Water for Injection or Purified Water to the bottle. Replace the cap tightly. Reconstituted solution is **0.05 mg/mL**.
2. Shake vigorously by inversion for at least two minutes to ensure complete powder reconstitution to a solution. Then place the bottle on a bench top or flat surface undisturbed for 5-10 minutes for any foam to dissipate.

3. Insert a 28 mm "**Press-In-Bottle Adapter (PIBA®)**" into the neck of the bottle. **Please ensure that the lip of the Adapter fits snugly with the top of the bottle.** Replace the cap tightly.
4. Immediately prior to the removal of dose for administration swirl the bottle of solution gently 2-3 times, if any foam appears allow the bottle to sit for at least 1 minute for the foam to dissipate.
5. Remove the required dose using a suitable graduated syringe:
 - a. Ensure that the syringe plunger is fully pushed into the barrel.
 - b. Insert the syringe tip into the Adapter, then invert the bottle and dispense at least 5 mL of solution into the syringe and then pump the entire solution back into the bottle to purge the syringe of any air bubbles. Repeat this step until the syringe is free from air bubbles.
 - c. Withdraw the required dosing volume. Then re-invert the bottle and remove the syringe from the Adapter and administer the dose to the patient as soon as possible.

Supplier: Trametinib is supplied by Novartis and distributed by CTEP, DCTD, NCI. **Do not use commercial supply.**

Obtaining the Agent

Agent Ordering

